2.3. Coding Versions

Adverse events, procedures, and non-drug therapies are coded using MedDRA 18.0. Medications and therapies are coded using WHO-DDE v2013 March.

2.4. Subgroup Analysis

Subgroup analyses for IGA and PGA success rate at Week 12, absolute change from baseline for inflammatory and non-inflammatory lesion counts at Week 12 on the face and trunk, treatment-emergent adverse events by SOC and PT, and local tolerability parameters worsened from baseline on the face and trunk will include an analysis by:

- Age: 9-11 years, 12-17 years, and ≥ 18 years of age
- Gender: female and male
- Age and gender: female < 25 years, male < 25 years, female ≥ 25 years, and male ≥ 25 years
- Race: White, Black or African American, Asian, and Other
- Ethnicity: Hispanic or Latino and Not Hispanic or Latino
- Skin Phototype: I-III and IV-VI

In addition, a subgroup analysis for IGA and PGA success rate at Week 12, treatment-emergent adverse events by SOC and PT, and local tolerability parameters worsened from baseline on the face and trunk will be provided for the additional age categories of: <14 Years, 14-17 Years, and >=18 Years.

2.5. Subpopulations

Three subpopulations of the ITT population will be studied using the primary and secondary efficacy analyses. Those populations are defined as:

- Subjects with at least 75% non-inflammatory baseline lesions. A subject's baseline total non-inflammatory lesion count will be divided by their baseline total lesion count (inflammatory and non-inflammatory). If the result is greater than or equal to 0.75, they will be included in the subpopulation. Presence of nodules and/or cysts will not be included for the calculation of inflammatory lesion counts.
- Subjects with no prior use of topical or oral retinoids. Use of topical and oral retinoids are identified using the ATC4 codes of D10AD and D10BA from the concomitant medication dataset.
- Subjects with no prior use of medications for acne. Subjects with use of prior medication of acne are identified using the following indication terms from the concomitant medications dataset:
 - ACNE
 - ACNÉ
 - ACNE ULGARIS
 - ACNE CONGLOBATA
 - ACNE FACE WASH
 - ACNE FACE/CHEST/BACK
 - ACNE ON FACE
 - ACNE VULARIS
 - ACNE VULGARIS
 - ACNE VULGARIS AND PITYROSPORUM FOLLICULITIS
 - ACNE VULGARIS OF FACE
 - ACNE VUOLGARIS
 - ACNE WASH
 - AKNE VULGARIS
 - FACIAL ACNE
 - FACIAL ACNE VULGARIS

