6 SAMPLE SIZE CONSIDERATION

The assumptions used to power this study are based on the phase 2 study (SPR18223). Success rates based on IGA are assumed 23% (CD5789) and 15% (Vehicle). For a 90% power to detect a significant difference versus vehicle using a two-sided test at a type I error of 0.05, 504 subjects per arm are needed for analysis. To compensate for drop-outs and non-evaluable subjects (estimated at 16%), a total of 1200 subjects are to be randomized (600 per arm).

Based on the results from stratum 1 in the phase 2 study (SPR18223), the mean difference between the active and vehicle is estimated at 3 inflammatory lesions and 6 non-inflammatory lesions. Standard deviation of changes in lesion counts, based on phase 2 and on large phase 3 trials from other projects are estimated at 12 for inflammatory lesions and 20 for non-inflammatory lesions. Using these as assumptions and a sample of 504 evaluable subjects per arm, power is above 95% for both lesion types.

The assumptions for truncal acne being the same as for facial acne in terms of efficacy, therefore it is estimated that the power for truncal acne is adequate.

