7 STATISTICAL METHODS AND DATA CONSIDERATIONS

For statistical analyses purpose, baseline is defined as the last measurement prior to the first application of the study drug.

A type I error of 0.05 (two-sided test) will be used to declare statistical significance.

In general, no formal inferential analyses are planned for the baseline and safety data, and only summary statistics will be provided.

For the summary statistics, the categorical variables will be summarized by frequency and percentage for each response category (N, %); and the continuous variables will be summarized using means, medians, minimum, maximum, and standard deviations.

SAS version 9.3 or above will be used for all statistical analyses.

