c. Subjects with missing IGA/PGA data at Week 12 will be considered as ‘failures’ for IGA/PGA success rate; and subjects with missing lesion counts data at Week 12 will be assigned the median change of lesion counts data from subjects who are ‘failures’ of IGA/PGA success within the same treatment group.

7.4.2.3 *Interim analyses and data monitoring*

No interim analysis is planned for this study.

7.4.2.4 *Multicenter studies*

A small center is defined as the center which randomizes less than 8 subjects. Small centers will be pooled prior to analyses. First, centers will be sorted by country, number of randomized subjects (descending order) and center number (ascending order). Pooling will start with combining the largest of the set of small centers with the smallest center within that country. If there is a further need to combine data (the size of the pooled centers includes less than 8 subjects), the next smallest center will be combined with the next largest of the small centers, until the criterion of a minimum of 8 subjects is met. The process will continue until all pooled centers have a minimum of 8 subjects within the country. Any remaining centers will be pooled with the last pooled center within the country. The pooled centers will be referred to as ‘analysis centers’ in the statistical analyses.

7.4.2.5 *Multiple comparison/multiplicity*

Control of type 1 error, the experiment-wise error rate is controlled at alpha level of 0.05.

No adjustment for multiplicity is required for the primary efficacy endpoint as the statistical significance needs to be met for all 3 co-primary endpoints.

The statistical inferential testing for the secondary primary efficacy endpoint is conditional on the statistical significance of the primary efficacy endpoint, and all 3 co-secondary efficacy endpoints are required to reach statistical significance for the secondary efficacy endpoint to be statistically significant.

Therefore, no adjustment for multiplicity is required in this study.

7.4.2.6 *Use of an efficacy subset of patients*

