The ITTT population is potentially a subset of the ITT population with moderate truncal acne at the Baseline visit. In practice, this excludes from the ITT population the children between 9 and 11 years old who did not meet inclusion criterion #4 (PGA) or #5 (Truncal lesion counts) at study entry (i.e. who do not have PGA of 3, at least 20 inflammatory lesions on the trunk and at least 20 non-inflammatory lesions on the trunk).

The PP/PPT Population will be determined prior to breaking the study blind using the criteria described in Section 5.5.

7.4.2.7 *Active-Control studies intended to show equivalence*

Not applicable.

7.4.2.8 *Examination of Subgroups*

All subgroup analyses are exploratory in nature.

To determine whether the treatment effect is consistent across various subgroups, the estimate of the between-treatment effect (with a nominal 95% CI) for the primary efficacy endpoint will be estimated and plotted within each category of the following classification variables:

- Age Group [<18 years (“9-11 years”, “12-14 years”, “15-17 years”), ≥18 years (“18-64 years”, “≥65 years”)]
- Gender (female, male)
- Race (white, non-white)
- Country (US, Canada)
- Skin Phototype (I-III, IV-VI)

Treatment effects and nominal 95% confidence intervals by category for the classification variables listed above will be reported as well as presented graphically. Formal statistical testing of these interactions will not be performed.

For success rate on IGA, treatment effects and the nominal 95% confidence intervals will be summarized by category for the subgroup variable using the same method as the primary analysis.

For the change in lesion counts by type, treatment effects and the nominal 95% confidence intervals will be summarized by category for the subgroup variable using two-sample t-test.

7.5 **Safety analysis**

All safety analyses are descriptive, and no formal inferential testing will be performed.

7.5.1 **Extent of exposure**

7.5.1.1 *Study Duration*

Study duration (day) is defined as the date of the last visit minus the date of the Baseline visit plus one. Study duration will be summarized by descriptive statistics using the ITT population.

7.5.1.2 *Treatment Duration*

Treatment duration (day) is defined as “the date of the last application on face or the trunk, whichever is later, minus the date of the first application on face or the trunk, whichever is earlier, plus one”.

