2.6. Site Pooling

Analysis centers will be created by totaling the number of subjects at each site and pooling smaller sites together.

Sites with fewer than 8 subjects will be pooled. Sites will be sorted by country, the number of subjects at that site in descending order, and then site number in ascending order. For each country separately, the site at the top of the list (the largest site with less than 8 subjects and, if tied, the smallest site number) will be pooled with the site at the bottom of the list (the smallest site with less than 8 subjects and, if tied, the largest site number). If the pooled site now has at least 8 subjects, it is removed from the list.

Otherwise, it will continue to be combined with the smallest available site until it has at least 8 subjects or no sites remain.

After all possible pooling is done, if all remaining small sites cannot be pooled together into an analysis center with at least 8 subjects, those sites will all be pooled into the analysis center created in the previous iteration of the pooling, even if that analysis center is not the smallest. If there was no other pooling done (because all small sites in the country total to less than 8 subjects), those sites will be pooled with the smallest site in the country. If no other sites are available in that country, the site will remain with fewer than 8 subjects.

3. Protocol Deviations

Protocol deviations will be provided in the DV SDTM dataset. Subjects with a deviation categorized as "Major" or "Major for face" will be excluded from the PP population. Subjects with a deviation categorized as "Major," "Major for face," or "Major for trunk" will be excluded from the PPT population.

The number of subjects in each analysis population will be summarized, and specific protocol deviations will be summarized in a listing.

4. Disposition

For the purposes of disposition summaries, subjects are considered to be Screened if they have signed the Informed Consent form. Subjects will be considered randomized once they've been assigned a treatment.

5. Prohibited Medications

Prohibited medications will be flagged on the concomitant medications listing. A list of prohibited medications with ATC/Drug names will be identified prior to the database lock.

6. Efficacy Analyses

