6.8. Efficacy Subgroup Analysis

The subgroup analyses will repeat the analysis of the three co-primary and co-secondary endpoints on all subgroups. The MAR multiple imputation method will be used to handle missing data.

For lesion count subgroup analysis, the t-tests will be done assuming unequal variances using Satterthwaite's formula for variance.

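### The three subpopulations reuse analysis centers pooled on whole-trial counts, so the center-stratified CMH and the center-adjusted ANCOVA lose much of their information if a subpopulation is small

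*SAP*

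**What the plan says.** - **How centers are formed.** SAP 7.4.2.4: "A small center is defined as the center which randomizes less than 8 subjects". Addendum 2.6 gives the algorithm: "Analysis centers will be created by totaling the number of subjects at each site and pooling smaller sites together". Pooling stays within country. Neither section mentions pooling again inside a subset.
- **What the centers are used for.** SAP 7.4.1.1 (with the notes to Table 1) stratifies the CMH test by analysis center and puts analysis center in the ANCOVA. The success-rate difference and its 95% interval are unstratified (SAP 7.4.1.1, Addendum 6.1 and 6.2).
- **Subpopulations.** Addendum 2.5: "Three subpopulations of the ITT population will be studied using the primary and secondary efficacy analyses". The three are subjects whose baseline lesions are at least 75% non-inflammatory, subjects with no prior retinoid use, and subjects with no prior acne medication.
- **Subgroups.** SAP 7.4.2.8 says that IGA success "will be summarized by category for the subgroup variable using the same method as the primary analysis", and calls all subgroup analyses exploratory. For lesion counts it plans a two-sample t-test. Addendum 6.8 adds: "The subgroup analyses will repeat the analysis of the three co-primary and co-secondary endpoints on all subgroups". It then specifies unequal-variance t-tests for the lesion counts.
- **Number of sites.** About 160 in the protocol synopsis; about 70, with about 17 subjects each, in SAP section 2.

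**The concern.** The 8-subject minimum exists so that strata normally contain both arms. It does this for the full trial but not for a subset. When 60 to 120 subjects are scattered over many centers, a large share of the strata hold a single subject or a single arm. Such a stratum contributes zero to the CMH statistic. In the ANCOVA it contributes nothing to the treatment contrast and still uses up a parameter.

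A subpopulation p-value or ANCOVA interval could then look uninformative because of how the strata were built rather than because the effect is absent. For IGA/PGA success, one table row could also pair an interval based on every subject in the subset with a p-value based only on those in two-arm strata.

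**Working it through.** **The plan's own figure.** SAP section 6 assumes success rates of 23% and 15% with 90% power, and says that "using a two-sided test at a type I error of 0.05, 504 subjects per arm are needed for analysis". With pooled variance and no continuity correction:

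n = [1.960·√(2·0.19·0.81) + 1.2816·√(0.23·0.77 + 0.15·0.85)]² / 0.08² = 503.3, so 504 per arm; 504/0.84 = 600 per arm.

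This reproduces. The documents state no number of analysis centers, no subset sizes and no information loss, so the rest needs assumptions.

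**Number of centers.** The Addendum 2.6 rule was simulated with 1200 subjects, blocks of 4 and site sizes from equal to widely spread (8 countries assumed).
- 160 sites: on average 90 to 116 centers, about 97-103 for moderately spread site sizes.
- 70 sites: on average 51 to 70 centers, about 58 for moderate spread.

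**Information kept.** With a and b subjects per arm in each stratum, the share kept is Σ ab/(a+b), divided by the same quantity for the unstratified subset. For K equal, balanced strata of M subjects and a random subset of N, this is approximately

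[M/(M−1)] · (1 − E/N), where E = K(1 − e^(−N/K)) is the expected number of non-empty strata.

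Take K = 100 and M = 12. The ANCOVA residual df are N − E − 2, against N − 3 without center. The interval ratio is √(1/share) times the ratio of the t quantiles.

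| N | E | share kept | residual df | t with / without center | interval ratio |
|---|---|---|---|---|---|
| 60 | 45 | 27% | 13 | 2.162 / 2.002 | 2.1 |
| 120 | 70 | 46% | 48 | 2.011 / 1.980 | 1.5 |
| 140 | 75 | 50% | 63 | 1.999 / 1.977 | 1.4 |
| 200 | 86 | 62% | 112 | 1.981 / 1.972 | 1.3 |
| 300 | 95 | 75% | 203 | 1.972 / 1.968 | 1.16 |

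Simulating the pooling rule with 160 sites of moderately spread size gives closely similar values: about 27-29% at 60, 46-48% at 120 and 73-75% at 300. With 70 sites and about 58 centers, about 45% is kept at 60 and 64% at 120. Half or more is therefore lost only below about 140 subjects (160 sites) or roughly 60-100 subjects (70 sites).

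**Effect on the CMH test.** Simulated power with 100 strata of 12 and no imputation, stratified against unstratified:
- 23% vs 15% success: 4% vs 13% at N = 60; 12% vs 20% at N = 120; 33% vs 42% at N = 300.
- An assumed larger effect, 40% vs 15%: 14% vs 58% at N = 60; 53% vs 89% at N = 120; 98.9% vs 99.9% at N = 300.

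**Which subpopulation could be that small.** Inclusion criterion 3 requires at least 20 inflammatory facial lesions. If the ratio is taken on the face, 75% non-inflammatory means at least 3 × 20 = 60 non-inflammatory lesions. How many subjects qualify depends on baseline distributions that the documents do not give. With assumed mean counts of 30-38 inflammatory and 45-60 non-inflammatory, one set of lognormal assumptions gives 33-90 subjects. Varying the SDs (10-18 and 20-40) and the correlation (0-0.5) gives 11-191. The sizes of the two no-prior-use groups cannot be derived.

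**After re-pooling within the subset.** Strata of at least 8 lose about 1/8 at most. For example, 100 subjects in about 12 strata keep 1 − 12/100 = 88%, against 40% with K = 100. Simulation with within-country pooling and countries of very unequal size keeps about 85-92% for N of 60 to 300.

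**The case against.** The strongest reply is that little depends on this. The subpopulations lie outside the testing sequence and the subgroups are declared exploratory. The primary analysis keeps about 99-100% of its information, and detailed specifications are deferred to table shells finalized before database lock (SAP section 9). All of that stands. It limits the importance of the point, but the addendum still gives a rule that performs poorly in a small subset and offers no alternative.

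Several stronger readings are tempting and are not supported:
- *Subgroup lesion counts suffer too.* The opening sentence of Addendum 6.8 might suggest that the ANCOVA is repeated in subgroups. The same section and SAP 7.4.2.8 specify t-tests, which have no center term.
- *Subgroup effect estimates lose precision.* The success-rate difference and interval are unstratified. Only a subgroup CMH p-value, if one is reported, depends on the strata.
- *There are about 100 strata.* That needs the protocol's 160 sites; the SAP's 70 give about 58.
- *The 75% group must be small.* A floor of 60 lesions does not fix its prevalence, and facial non-inflammatory counts have no upper limit.

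The calculation also assumes no center effect, the case in which adjusting for center can only cost. A real center effect would recover part of the loss.

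Against the remedy, Addendum 2.6 pools only within country, so some strata may stay below 8. The simulation with unequal countries allowed for this and still kept about 85-92%.

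**Conclusion.** The point holds for the CMH and ANCOVA of the three subpopulations, and for the IGA/PGA subgroup CMH p-values if reported. As written, these use strata sized for the whole trial, and the cost depends on subset size. At 160 sites it ranges from roughly a quarter of the information at 300 subjects to nearly three quarters at 60. At 70 sites it is about 55% at 60 subjects and 36% at 120. These figures assume random spread of subset members over centers and no center effect.

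The group with at least 75% non-inflammatory lesions may fall in the range where half or more is lost; the two no-prior-use groups may not. A reader might infer that the trial's main conclusions, or all its subgroup results, are at risk. They are not. This is a cheap improvement to secondary-tier analyses, best settled before unblinding so that the stratification is not chosen with results in view.

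**What to change.** - **Addendum 2.5:** state that, for each subpopulation, the 2.6 pooling algorithm is re-run on that subset's own subject counts and the resulting strata are used for its CMH and ANCOVA. If fewer than two strata of at least 8 subjects can be formed, no center term is used.
- **Addendum 6.8:** apply strata formed in the same way to the IGA/PGA subgroup CMH only, and leave the lesion-count t-tests as planned.
- **Site numbers:** reconcile the protocol's 160 sites with the SAP's 70, since the size of the problem depends on which applies.

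The cost is a few lines of text and a re-run of an algorithm already specified. The downside is coarser control of center differences and center definitions that vary between subsets and differ from those of the primary analysis, which is acceptable for exploratory work.

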9. The subject has clinically significant abnormal laboratory values according to the Investigator at Screening (to be checked prior to Baseline).
10. The subject has known or suspected allergies or sensitivities to any components of any of the study drugs (see Investigator's Brochure).
11. The subject is a female who is lactating.
12. The subject is a female who intends to conceive a child during the trial or within 1 month after the last study drug application.
13. The subject is currently participating in any other clinical trial of a drug or device OR past participation in any other clinical trial within the 30 days prior to the Baseline visit.
14. The subject was previously or is currently enrolled in the long term safety study RD.03.SPR.18250 conducted by Galderma.
15. The subject has received, applied, or ingested the following treatments within the specified time frame prior to the Baseline visit as defined in below:

Treatment restrictions

Topical treatment on the face and trunk:	
Antibiotics Benzoyl peroxide Azelaic acid Zinc Corticosteroids Other topical treatments (including laser)	2 weeks
Retinoids	4 weeks
Topical procedures on the face and trunk:	
Phototherapy devices for acne (e.g., ClearLight™) Adhesive cleansing strips (e.g., Pond®, Biore®) Cosmetic procedures (i.e., facials, peeling, comedone extraction)	1 week
Systemic treatment:	
Non-steroidal anti-inflammatory drugs ¹	2 weeks
Corticosteroids (except inhaled corticosteroids or intrathecal corticosteroids)	4 weeks
Antibiotics (except plain penicillin)	4 weeks
Oral retinoids	6 months
Immunomodulators, including biologics	6 months

Note:

1) During the study, the use of Non-steroidal Anti-Inflammatory Drugs (NSAIDs) is acceptable for up to 21 days (cumulative) of treatment; however, it should be avoided during the 1 week period prior to the final study assessment.

No time frame period is specified for Alpha-hydroxy acid products, medicated shaving creams, after-shaves, colognes, astringents, or preparations with alcohol, but their application is prohibited during the study.

16. The subject has been exposed to excessive ultraviolet (UV) radiation within one month prior to the Baseline visit or the subject is planning intense UV exposure during the study (i.e., occupational exposure to the sun, sunbathing, tanning salon use, phototherapy, etc.)

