	Screening Visit ¹ (maximum 14 days+3 days prior to Baseline)	Baseline Visit	Week 1 Visit (±3 days)	Week 2 Visit (±3 days)	Week 4 Visit (±3 days)	Week 8 Visit (±3 days)	Week 12 Final/ET Visit ² (±5 days)
Skin Oiliness Scale (SOS) Questionnaire ¹¹		X					X
Self-assessment of facial acne improvement							X
Study drug(s) Dispensing (D) and Accountability (A)		D			D/A	D/A	A
Moisturizer/cleanser Dispensing (D)		D ¹⁰					
Dosing calendar Dispensed (D) returned and reviewed (RR)		D	RR	RR	RR	RR	RR
Exit Form ¹¹							X

- (1) Baseline visit must be performed maximum 14 days after Screening with a time window of +3 days. For women of childbearing potential, there must be at least 14 days between Screening and Baseline visits (for UPT reason). No re-screening will be allowed.
- (2) Week 12 procedures will be performed earlier in case of study discontinuation.
- (3) Confirm information at Baseline
- (4) For subject of childbearing potential only: Urine Pregnancy Tests will be performed at Screening, Baseline, Week 4, Week 8, Week 12. For pre-menstrual subjects re-confirm pre-menses status at every visit and in case of status change collect information on contraceptive method and perform a UPT. For the ones who begin menses after the Screening visit, urine pregnancy tests will be performed at the visit where there was a change in status and according to the schedule for females of childbearing potential (Baseline, Week 4, 8, 12/ET). Additional UPTs may be performed at the Investigator's discretion.
- (5) Subjects 9 to 11 years of age who did not meet the criteria for moderate truncal acne at Baseline: PGA will be evaluated after baseline to allow the investigators to decide to start the treatment on the trunk if the subject develops truncal acne during the study whatever the PGA grade. Local tolerability will be assessed. The Lesion counts will not be evaluated.
- (6) Photos are not mandatory; subjects will be able to participate in the study even if they refuse to participate in photo procedures.
- (7) Collection of Adverse Events will begin after signing of the informed consent/assent form.
- (8) Medication that continues after Screening visit should be recorded on the Concomitant Medication page of the eCRF. Medical or surgical procedures occurring after Screening visit should be recorded on the Procedures page of the eCRF

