7.3 Medical history, previous and concomitant therapies/procedures

For statistical analysis purposes, previous therapies/procedures are defined as those ending at Baseline visit or before; and concomitant therapies/procedures are defined as those ongoing at the Baseline visit or starting after the Baseline visit.

Previous and concomitant therapies will be coded using WHODRUG dictionary. Previous and concomitant procedures will be coded using MedDRA dictionary.

A summary table will be provided for each of the following in the ITT population:

1. number and percentage of subjects who had previous therapies/medications by ATC text and WHO drug name
2. number and percentage of subjects who had concomitant therapies/medications by ATC text and WHO drug name
3. number and percentage of subjects who had previous procedures by System organ class and preferred term
4. number and percentage of subjects who had concomitant procedures by System organ class and preferred term

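### Addendum 2.5 defines the two 'no prior use' subpopulations from the concomitant medication dataset with no date limit, so subjects who first use such a product after Baseline are removed as prior users

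*SAP*

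**What the plan says.** SAP Addendum 2.5 lists three subpopulations of the ITT population in which the primary and secondary efficacy analyses are to be run. The first is fixed by baseline lesion counts. The second is labelled "Subjects with no prior use of topical or oral retinoids", and its rule reads "Use of topical and oral retinoids are identified using the ATC4 codes of D10AD and D10BA from the concomitant medication dataset". The third is subjects with no prior acne medication: "Subjects with use of prior medication of acne are identified using the following indication terms from the concomitant medications dataset", followed by a list of 16 terms. No start date, stop date or look-back period is given for either medication rule.

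SAP 7.3 treats previous and concomitant as separate categories: "previous therapies/procedures are defined as those ending at Baseline visit or before", whereas "concomitant therapies/procedures are defined as those ongoing at the Baseline visit or starting after the Baseline visit".

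In the protocol's schedule of assessments, previous therapies and concomitant therapies are separate rows, the former collected at Screening and the latter from Baseline on. Note 8 to the schedule adds: "Medication that continues after Screening visit should be recorded on the Concomitant Medication page of the eCRF".

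**The concern.** Prior use is a property that a subject has or lacks before treatment starts. The rule looks for it in a dataset named for the other category and sets no cut-off in time. Two errors could follow: removing subjects who took a retinoid or acne drug only during the trial, and keeping subjects who really were prior users.

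The first is the more serious in principle. A subject may start another acne product because the study cream is not working or is poorly tolerated, and that can differ between arms. The plan anticipates on-study use: SAP 5.5 lists interfering concomitant therapy as a possible reason for exclusion from the Per Protocol population, and Addendum section 5 flags prohibited medication on the concomitant medications listing. Under the written rule, a Per Protocol type of exclusion enters a group presented as a baseline-defined part of the ITT population. A statement about efficacy in retinoid-naive subjects would then rest on a group selected partly by what happened after randomization.

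**Working it through.** The plan gives no size, power or alpha for these subpopulations, so there is no figure to reproduce. The check has two parts.

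**1. Timeline for eligible subjects.** Inputs:
- Exclusion criterion 15 ("The subject has received, applied, or ingested the following treatments within the specified time frame prior to the Baseline visit"): topical retinoids 4 weeks = 28 days; oral retinoids 6 months, taken here as 182 days; topical antibiotics, benzoyl peroxide and azelaic acid 2 weeks = 14 days.
- Schedule note 1: "Baseline visit must be performed maximum 14 days after Screening with a time window of +3 days". Longest Screening-to-Baseline interval = 14 + 3 = 17 days.

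Minimum time between stopping and Screening = washout - longest interval:
- Topical retinoid: 28 - 17 = 11 days before Screening.
- Oral retinoid: 182 - 17 = 165 days before Screening.
- Topical antibiotic, benzoyl peroxide or azelaic acid: 14 - 17 = -3, so use can continue up to 3 days past Screening.

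Every retinoid user who met the washout had therefore stopped before Screening. The use is previous under SAP 7.3 and does not belong on the Concomitant Medication page. The same does not follow for acne products with a 2-week washout, which may reach that page. Nor does it follow for oral contraceptives approved as acne treatments, which inclusion criterion 8 allows at a stable dose and which may be ongoing.

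**2. Example records under two readings of the dataset.** Reading A: it holds only concomitant records as SAP 7.3 defines them. Reading B: it holds all medication records. Days are relative to Baseline. The last column counts only records that start before first application, in a source that includes previous therapies.

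| Record (matching code or term) | SAP 7.3 class | Truly prior? | A: removed? | B: removed? | Start-date rule: removed? |
|---|---|---|---|---|---|
| Topical retinoid, stopped day -28 | previous | yes | no (wrong) | yes | yes |
| Oral retinoid, stopped day -182 | previous | yes | no (wrong) | yes | yes |
| Benzoyl peroxide, stopped day -14 | previous | yes | no (wrong) | yes | yes |
| Started before Baseline, ongoing | concomitant | yes | yes | yes | yes |
| First started day +30 | concomitant | no | yes (wrong) | yes (wrong) | no |

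The last row is wrong under both readings. The first three rows are wrong under A only. The start-date rule classifies all five correctly.

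**The case against.** The best defence has three parts.

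*The dataset probably includes earlier medication.* The acne rule itself expects to find prior medication there. Addendum 2.2 sorts medications into concomitant or not by their dates, which suggests that records ending before treatment are held. The 16 indication terms, misspellings included, look like entered text and fit a dataset with past treatments, though they do not prove it. This stands: the name of an eCRF page does not settle what an analysis dataset contains. A reader might infer that true prior users are kept as a matter of fact, or that the 'no prior use' group is nearly the whole ITT population less on-study users of prohibited acne drugs. The documents do not support either statement. The first holds only under reading A. The second also overlooks acne products with a 2-week washout and stable oral contraceptives, which can be recorded as concomitant in eligible subjects.

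*The word prior supplies the date limit.* A careful programmer may well apply it, and SAP 9 places detailed specifications with the table shells, which are a separate document. But the retinoid identification sentence drops the word and gives only codes and a dataset. SAP 7.3 does not fill the gap cleanly either: its previous category requires the therapy to have ended by Baseline, so a product started earlier and still in use would not count as prior. The rule gives the intended group only with a condition that Addendum 2.5 does not state.

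*The impact is small.* This also stands. SAP 7.4.1.1, 7.4.1.2 and 7.4.2.5 confine the confirmatory tests to the co-primary and co-secondary endpoints in the ITT and ITTT populations.

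**Conclusion.** The point holds in two parts of different strength. Followed as written, Addendum 2.5 removes subjects whose first retinoid or acne-medication use came after Baseline, whichever records the dataset holds; only an unwritten date filter avoids this. Whether prior users are also wrongly kept depends on the dataset's content, which the documents leave open. If it is restricted to concomitant records under SAP 7.3, all retinoid users who met the washout and all acne-medication users who stopped by Baseline would be misclassified as having no prior use.

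The size cannot be given. The documents contain no count or rate of prior or on-study use, and dependence on arm is a possibility, not a finding. The 11-day figure assumes that the subject met the washout and applies to topical retinoids (oral retinoids follow more easily), not to acne medication in general. The consequence is limited to these supplementary analyses: type I error, the ITT and ITTT results and the superiority claims do not change. The correction is still worth making, because the stated source and rule give the wrong group when applied literally.

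**What to change.** In Addendum 2.5:
- Name the source and state that it includes both previous and concomitant medication records.
- Count as prior use only matching records with a start date before the first study drug application; ignore records that start on or after it. This agrees with SAP section 7, which takes baseline as the last measurement before first application. It differs on purpose from SAP 7.3, which classifies by the Baseline visit and, for previous therapies, by end date; the addendum should say so.
- State how partial or missing start dates are treated for this purpose. Addendum 2.2 settles only whether a medication is concomitant.
- Apply the same rule to the ATC codes and to the acne-indication list.

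The cost is a few sentences and a date filter in the derivation, with no new data. If the derivation already works this way, only the text needs to change.
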